1.1.2. Asthma

Infant respiratory viral infection and childhood asthma are the most common acute and chronic diseases of childhood, respectively. Common clinical features and links between these diseases have long been recognized, with early-life RSV LRTIs being strongly associated with increased asthma risk.

Although asthma is probably a heterogeneous disease or syndrome, three factors and/or events consistently emerge for their ability to significantly influence asthma inception in the first decade of life: immune response aberrations, which appear to be defined best by the concept of cytokine dysregulation; LRTIs, in particular RSV; and some form of gene–environment interaction that needs to occur at a critical timeperiod in the development of the immune system or the lung [Lemanske, 2002].

Population-level contribution of RSV LRTIs is best demonstrated by the populationattributable risk for asthma after these early-life LRTIs. Among infants, the cumulative incidence of LRTI is approximately 18 to 32% in the first year of life and approximately 9 to 17% in the second year of life. Among infants with LRTI, the prevalence of RSV can be as high as 80%, especially in the first 3 months of life. Thus, the phenotype of asthma after infant RSV LRTI accounts for up to 31% of early childhood asthma, with a population-attributable risk estimated at about 13% in several diverse populations [Feldman, 2015].

Numerous longitudinal studies have demonstrated this first important line of evidence that RSV LRTIs precede the development of asthma. Several birth cohort studies also demonstrate a dose–response relationship between infant respiratory viral infection severity and asthma risk, with increasing infant infection severity associated with greater childhood asthma risk and asthma severity [Feldman, 2015].

The Childhood Origins of Asthma (COAST) study was developed to determine and define the importance of these three factors on asthma pathogenesis and to test different asthma case classifications [Lemanske, 2002; Lemanske, 2005; Bisgaard, 2011; Jackson, 2008; Jackson, 2012; Bønnelykke, 2015]. These studies have used similar albeit slightly different case definitions on asthma diagnosis. The International Study of Asthma and Allergies in Childhood (ISAAC) takes a slightly different parentbased questionnaire approach toward assessing asthma prevalence in young children.

These definitions are widely used in epidemiological literature of asthma etiology in children. The Bisgaard definition [Bisgaard, 2011] has multiple criteria that are assessed by the physician from records. Therefore the advantage of this definition is that the same objective criteria are applied to ascertain each case of asthma. However, its application may be challenging in some settings if routine medical records do not fully capture the necessary information in source. The Jackson definition [Jackson, 2008] includes the criteria of health care provider (HCP) diagnosis of asthma and prescription of β^2 agonists. This definition is therefore influenced by any differences in local practice of asthma diagnosis and management of wheeze. However, its advantage is that it captures the reality of diagnosis and treatment. ISAAC uses simple, robust, primarily symptom-based questions that are administered solely to the parents. ISAAC's strength is that its definitions are not affected by differences in local asthma treatment practices; however, its lack of clinical case confirmation may decrease its precision. The ISAAC questionnaire has been used to assess pediatric asthma prevalence in at least 42 countries across the globe [Pearce, 2007].

1.2. Rationale for the study (Amended 15-DEC-2017)

This study aims to assess the incidence and associated healthcare utilization of RSVassociated, suspected LRTI in a general population of infants from birth up to 2 years of age, and also to assess the accuracy of a newly developed LRTI case definition and severity scale, compared to two existing scales developed by *the* World Health Organization (WHO) [*Modjarrad*, 2016] and [Nokes, 2008].

This study will also assess the extent to which RSV LRTI in early life (up to 2 years of age) accounts for the total burden of wheeze and asthma up to the sixth birthday, and test the performance of 3 asthma case definitions – those of Bisgaard, Jackson, and ISAAC.

The LRTI case definition and severity scale to be used in this study has been developed as a consensus model derived from existing definitions in the literature, and existing guidelines by GlaxoSmithKline (GSK) clinical staff, taking into account the advice of a panel of international RSV experts.

Considering asthma case definitions, this study anticipates that Bisgaard will be more specific and Jackson more sensitive. Although it is likely that the ISAAC symptombased case definitions will be the most sensitive and least specific of all three definitions [Yang, 2011], its incorporation will facilitate wider international results comparisons. Hence, this study will assess the performance of the different case definitions since this will help planning for phase 3 clinical trials of RSV vaccines.

If, in future, a maternal and/or pediatric RSV vaccine is introduced, results of this study may be used to evaluate post-vaccination incidence reduction (in RSV LRTI and/or wheeze and asthma) and the vaccine's potential public health impact.

2. OBJECTIVES (AMENDED 15-DEC-2017)

2.1. Objectives for the Primary Study (first 2 years)

2.1.1. Co-Primary objectives

In a cohort of infants followed-up from birth up to 2 years of age:

• To determine the total health burden* of RSV-associated RTI with a suspicion of involvement of the lower respiratory tract..

*Health burden refers to burden of the disease imposed on the study population in terms of incidence of the disease and associated healthcare utilization in any healthcare setting.

• To assess the performance of the LRTI case definition and severity scale for RSV associated cases.

Refer to Section 4 for the list of clinical parameters included under each LRTI case definition under LRTI case definitions for data analysis.

Refer to Section 9.1.1 for the definition of the co-primary endpoints.

2.1.2. Secondary objectives

In a cohort of infants followed-up from birth up to 2 years of age;

- To determine the total health burden of non-RSV-associated RTI with a suspicion of involvement of the lower respiratory tract.
- To evaluate the association between RSV-associated LRTI, RSV-associated severe LRTI and RSV neutralizing antibodies in the baseline cord blood samples collected from subjects, at birth.
- To determine the prevalence of RSV infection, at 2, 4, 6, 12, 18 and 24 months in a randomly selected sub-cohort of subjects by assessing antibodies in serum.
- To assess the between calendar year variability in the incidence rates of RSV-associated LRTI.

Refer to Section 9.1.2 for the definition of the secondary endpoints *for the primary study*.

2.1.3. Tertiary objectives

In a cohort of infants followed-up from birth up to 2 years of age:

- To explore the association of co-infections with the incidence of RSV-associated LRTI and/or severe LRTI (as determined by the LRTI case definition and severity scale) using xTAGTM respiratory viral panel (RVP) fast assay.
- To explore the association of RSV and other respiratory viruses with the incidence of LRTI and/or severe LRTI (as determined by the LRTI case definition and severity scale) using xTAGTM RVP Fast assay.
- To explore the association of RSV viral load with the incidence of RSV-associated RTI, LRTI and/or severe LRTI (as determined by the LRTI case definition and severity scale).
- To explore the impact of changes to the symptoms and threshold levels of symptoms in the LRTI case definition and severity scale.
- To assess the impact of potential RSV risk factors (e.g. complications at birth, family history of respiratory disease, living environment and household composition, breast feeding, passive smoking, day care attendance) on the incidence and severity of RSV-associated LRTI.
- To explore the impact of variations in cord-blood sample collection variables on the stability of test results.
- To assess the natural decay of maternal antibody levels using a single follow-up blood sample collected from a randomly selected sub-cohort of subjects at 2, 4, 6, 12, 18 and 24 months.

Refer to Section 9.1.3 for the definition of the tertiary endpoints *for the primary study*.

2.2. Objectives for the Extension study (Approximately 2 years of age to 6th birthday)

2.2.1. Primary objectives

None

2.2.2. Secondary objectives

In a cohort of infants followed-up from birth up to 6 years of age:

- To determine the population attributable risk of recurrent wheeze and asthma from birth to sixth birthday associated with RSV clinical LRTI in the first two years of life.
- To determine the population attributable risk percent of recurrent wheeze and asthma from birth to sixth birthday associated with RSV clinical LRTI in the first two years of life.

Refer to Section 9.2.2 for the definition of the secondary endpoints for the extension study.

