9.2. Endpoints for the Extension Study

9.2.1. Primary: none

9.2.2. Secondary:

- Occurrence of medically attended wheeze
- Occurrence of wheeze or asthma requiring hospital admission.
- *Use of* prescription medications for wheeze or asthma.

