9.2.3. Tertiary

- Number of children with asthma (case definition 1) at age 2, 3, 4, 5, and 6 years of age
- Number of children with asthma (case definition 2) at age 2, 3, 4, 5 and 6 years of age.
- Number of children with asthma (case definition 3) at 3, 4, 5 and 6 years of age.
- Number of children with recurrent wheeze.

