9.8. Analysis of Objectives for the Extension study

9.8.1. Primary objectives: none

9.8.2. Secondary objectives

Data for secondary endpoints may be pooled across the primary and extension periods. Additional details are provided in the SAP.

9.8.2.1. To determine the population attributable risk of wheeze and asthma from birth to sixth birthday due to RSV clinical LRTI in the first two years of life.

The incidence rate of medically attended wheeze, wheeze or asthma requiring hospital admission, and prescription of medications for wheeze or asthma may be calculated and stratified by country.

The population attributable risk *may be* calculated by subtracting the incidence rate in the subjects who did not have RSV clinical LRTI in the first two years of life from the incidence rate in all subjects including both who had and who did not have RSV clinical LRTI in the first two years of life.

Details will be provided in the SAP. An example follows.

The population attributable risk of medically attended wheeze may be calculated as:

Ip-Iu

Where Iu is the incidence rate of medically attended wheeze in subjects who did not have RSV clinical LRTI in the first two years of life, and Ip is the incidence rate of medically attended wheeze in all subjects including both who had and who did not have RSV clinical LRTI in the first two years of life. *The above population attributable risk formula may be further adapted to best accommodate the data and their required analytic assumptions (e.g., a modified formula may be used for population attributable risk calculations involving recurrent outcomes).*

9.8.2.2. To determine the population attributable risk percent of wheeze and asthma from birth until sixth birthday due to RSV clinical LRTI in the first two years of life.

The population attributable risk percent together with 95% CI of medically attended wheeze, wheeze or asthma requiring *hospital* admission, and prescription of medications for wheeze and asthma *may* be calculated overall and by age strata (0-2 years, 2-4 years and 5-6 years), respectively.

The population attributable risk percent *may be* calculated by dividing the population attributable risk by the incidence rate in all the subjects including both who had and who did not have RSV clinical LRTI in the first two years of life.

For example, the population attributable risk percent of medically attended wheeze *may* be calculated as:

(Ip-Iu)/Ip*100

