9.8.3. Tertiary objectives

9.8.3.1. To explore the association of RSV clinical LRTI in the first two years of life and other potential risk factors for wheeze and asthma

Endpoints such as medically attended wheeze, wheeze or asthma requiring *hospital* admission, and prescription of medications for wheeze or asthma *may be calculated as recurrent events and* stratified by country.

Occurrence/recurrence rates will be calculated overall and by subgroups *for each of the outcomes, as relevant.* Multivaria*ble* Poisson regression *or other appropriate* models

including RSV clinical LRTI in the first two years of life and other potential risk factors such as, but not limited to, family history of asthma, and/or allergies, contact with pets, child history of allergy, eczema or atopic dermatitis, etc., will be explored, respectively.

9.8.3.2. To explore the performance of asthma case definitions.

The number and percentage of children with diagnosis of asthma (case definitions 1, 2, *and 3* will be described for each *applicable* age; the number and percentage of children with recurrent wheeze *at each applicable age* will be described overall and by country in frequency tables.

The risk of asthma at the age of 6 years using case definitions 1, 2 and 3 (occurring from 2^{nd} to the 6th birthday) will be analyzed using multivaria**ble** logistic regression model including RSV clinical LRTI in the first two years of life and other potential risk factors listed above, respectively.

- Statistical analysis of agreement will be performed to compare *asthma* case definitions *1*, *2*, *and 3 to each other*.
- Cohen's kappa *(or other appropriate)* coefficient *may be used for the comparisons*. The magnitude of the kappa coefficient represents the proportion of agreement greater than that expected by chance.

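### The extension's secondary objectives ask for the PAR and PAR% of recurrent wheeze and asthma, but the endpoints and PAR analysis they lead to name three other outcomes

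*Protocol*

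**What the plan says.** Protocol 2.2.2, repeated in the synopsis, gives the extension two secondary objectives and no primary one. The first is "To determine the population attributable risk of recurrent wheeze and asthma from birth to sixth birthday associated with RSV clinical LRTI", with exposure counted up to age 2. The second is the same for the percentage: "To determine the population attributable risk percent of recurrent wheeze and asthma from birth to sixth birthday associated with RSV clinical LRTI". The section then directs the reader: "Refer to Section 9.2.2 for the definition of the secondary endpoints for the extension study".

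Section 9.2.2 lists three endpoints: "Occurrence of medically attended wheeze", "Occurrence of wheeze or asthma requiring hospital admission", and use of prescription medication. Section 9.8.2.1 carries the same three into the PAR: "The incidence rate of medically attended wheeze, wheeze or asthma requiring hospital admission, and prescription of medications for wheeze or asthma may be calculated". Section 9.8.2.2 names them again for PAR%.

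The outcomes named in the objectives sit one level lower. Section 9.2.3 lists "Number of children with recurrent wheeze" and the number of children with asthma under each case definition. Section 9.8.3.2 gives frequency tables for both. For asthma it adds agreement statistics and a multivariable logistic model for "The risk of asthma at the age of 6 years using case definitions 1, 2 and 3", with RSV LRTI among the covariates.

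Section 9.8.2.1 leaves the details to the SAP. The supplied SAP (Amendment 1, section 2.1) states that it does not describe the extension analyses.

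**The concern.** A reader who starts at the objective and follows its own cross-reference arrives at endpoints that are not the ones the objective names. Followed as written, the listed PAR analyses leave both secondary extension objectives unanswered for recurrent wheeze and for asthma by any of the three definitions.

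The mismatch matters because of how the result would be used. Section 1.1.2 motivates the extension with a published population attributable risk for asthma of about 13%, and section 1.2 says the results may inform a future vaccine's public health impact. Without a specified PAR% for case-defined asthma, there is nothing to set beside that figure. If the choice is left until the data are in hand, it must be made among three asthma definitions, under text in 9.8.2 and 9.10 that already allows formulas and plans to be adapted.

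**Working it through.** No sample size, power or precision in the documents is tied to the PAR objectives, so there is no planned figure to reproduce. The check is a comparison of passages, followed by an illustration.

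**Step 1: objective against endpoint and analysis**

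| Outcome | Objective (2.2.2) | Endpoint level | PAR or PAR% in 9.8.2 | Other planned analysis |
|---|---|---|---|---|
| Recurrent wheeze | Named | Tertiary (9.2.3) | None specified | Frequency tables (9.8.3.2) |
| Asthma, definitions 1 to 3 | Asthma named | Tertiary (9.2.3) | None specified | Frequencies, agreement, logistic model (9.8.3.2) |
| Medically attended wheeze | Not named | Secondary (9.2.2) | Listed | Rates and regression (9.8.3.1) |
| Admission for wheeze or asthma | Not named | Secondary (9.2.2) | Listed | Rates and regression (9.8.3.1) |
| Prescription medication | Not named | Secondary (9.2.2) | Listed | Rates and regression (9.8.3.1) |

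The logistic model yields an odds ratio, which is not a PAR or a PAR%.

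**Step 2: are the outcomes interchangeable?** Table 5 shows that they are not.
- One provider-confirmed episode is enough for medically attended wheeze. Recurrent wheeze needs at least four episodes within a year, and these may be reported by parents alone. Neither outcome contains the other: a child with one confirmed episode meets only the first, and a child with four parent-reported, unconfirmed episodes meets only the second.
- The admission endpoint carries asthma in its name but is defined through provider-confirmed wheeze.
- Prescription medication overlaps with asthma definition 1, but it is not definition 1, 2 or 3.

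**Step 3: does other text supply the missing PAR?**
- Section 9.8.2.1 allows a modified formula where outcomes recur. This is permissive and names no endpoint. It fits 9.8.3.1, where the three listed endpoints may be counted as repeat events. Repeat-event counting is different from a four-episode phenotype.
- The title, section 3.1, section 3.2.2 and the headings in 9.8.2 speak of wheeze and asthma without the word *recurrent*. The passages therefore also disagree about what the objective is. Even under the shorter wording, case-defined asthma has no PAR.

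**Step 4: illustration of how far outcomes can differ.** The protocol's formula is (Ip − Iu)/Ip × 100. Let p be the proportion exposed and RR the ratio of exposed to unexposed incidence. Then Ip = Iu × [1 + p(RR − 1)], so

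PAR% = 100 × p(RR − 1) / [1 + p(RR − 1)].

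Both inputs are assumed, because the documents give neither for these outcomes.

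| p | RR 1.5 | RR 2 | RR 3 |
|---|---|---|---|
| 5% | 0.025/1.025 = 2.4% | 0.05/1.05 = 4.8% | 0.10/1.10 = 9.1% |
| 10% | 0.05/1.05 = 4.8% | 0.10/1.10 = 9.1% | 0.20/1.20 = 16.7% |
| 20% | 0.10/1.10 = 9.1% | 0.20/1.20 = 16.7% | 0.40/1.40 = 28.6% |

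Within this study p is the same whichever outcome is analysed, so the relevant comparison is along a row: two outcomes with different RR have different PAR%.

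**The case against.** The best defence is that the extension SAP has not been seen. Section 9.8.2.1 defers details to a SAP and offers medically attended wheeze as its worked example; 9.8.2.2 and the text after it defer the interval method in the same way. A reader might infer that the study will produce no attributable risk for recurrent wheeze or asthma. The documents do not support that. They show only that none is specified in what was supplied.

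A second defence is that the fault may be a single word. Most of the protocol says wheeze and asthma, which suits the three endpoints better, so *recurrent* in 2.2.2 and the synopsis may be what needs changing. This stands as an alternative reading and supports a second remedy. It does not remove the conflict, and it still leaves case-defined asthma without a PAR.

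A third is that the listed endpoints come closer to asthma than their names suggest. A reader might infer that the planned PARs capture only isolated early wheeze. That goes too far. Four of the five criteria in definition 1 concern medication, and any one criterion suffices, so the medication endpoint overlaps substantially with that definition. PAR% may also be calculated by age strata that include 2 to 4 and 5 to 6 years, and asthma under all three definitions is modelled against RSV LRTI. Overlap is still not identity, and an odds ratio does not answer a PAR objective.

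Finally, a reader might take the illustrative percentages as the size of an error in this study. They are not: every input is assumed.

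**Conclusion.** The concern holds in limited form. Section 2.2.2 and the synopsis name recurrent wheeze and asthma; the endpoint list they point to and the PAR text in 9.8.2 name three other outcomes. For recurrent wheeze and for asthma by definitions 1 to 3, no PAR or PAR% is specified in the supplied protocol or SAP. The passages also disagree on whether *recurrent* belongs in the objective.

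This is more than missing detail, because the stated endpoint list leaves both secondary objectives unanswered for the outcomes they name. The conclusion rests on the text alone and is subject to any separate extension SAP. The size of the consequence is unknown. The 2.4% to 28.6% range shows only that outcomes with different relative risks cannot substitute for one another.

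**What to change.** In 9.2.2 and 9.8.2, and in the extension SAP, add recurrent wheeze as defined in Table 5 and asthma by case definitions 1, 2 and 3 as PAR outcomes. For each, give PAR as Rp − Ru and PAR% as (Rp − Ru)/Rp × 100, with 95% CI. Here Rp is the proportion of all children, and Ru the proportion of unexposed children, who ever meet the definition.

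Use the objective's own window, birth to the sixth birthday, and the annual assessments available for each definition: from age 2 for definitions 1 and 2, from age 3 for definition 3. State any narrower window openly. Definitions 1 and 3 look back one year, so status at a single birthday is a period prevalence, not a cumulative incidence. State also which assessments were completed retrospectively, since enrolment in the extension may occur at any time up to the sixth birthday. Keep the three current endpoints as supporting PARs.

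Alternatively, reword 2.2.2 and the synopsis to match the three endpoints, and state that no PAR will be claimed for recurrent wheeze or case-defined asthma. Under either option, use one wording of the objective in the title, 2.2.2, 3.1, 3.2.2 and 9.8.2.

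The cost is protocol and SAP wording, a few more table rows, and wider intervals for the rarer outcomes. The study already derives these outcomes for its tertiary analyses, so no new data collection is called for.

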2.2.3. Tertiary objectives

In a cohort of infants followed-up from birth up to 6 years of age:

- To explore the association of RSV clinical LRTI in the first two years of life with other potential risk factors for wheeze and asthma.
- To explore the performance of asthma case definitions.

Refer to Section 9.2.3 for the definition of the tertiary endpoints for the extension study.

